### 1.3.1. Clinical Safety Experience with Azacitidine

As of 18 May 2016, approximately 19,685 subjects have been treated with azacitidine in clinical studies, with 2,049 in the Celgene development program worldwide (1,144 with azacitidine injectable, 717 with azacitidine oral, and 192 with injectable and oral azacitidine (please note that 3 subjects from AZA PH US 2007 CL005 and 1 subject from AZA PH US 2008 CL008 enrolled in roll-over protocol CC-486-GEN-001, are counted only once in the overall total), 8,656 through National Cancer Institute (NCI)-sponsored clinical studies in the US, and an estimated 8,980 in non-Celgene-sponsored studies globally. In addition, it is estimated that cumulative commercial exposure to azacitidine during marketing experience is 273,411 patients. Therefore, overall estimated cumulative exposure to azacitidine during clinical trials and commercial experience is 293,096 patients (Azacitidine Development Safety Update Report [DSUR] #12, data cut-off 18 May 2016).

The most commonly reported adverse reactions with azacitidine treatment were hematological reactions including anemia, thrombocytopenia, neutropenia, febrile neutropenia, and leukopenia, gastrointestinal events including nausea, vomiting, abdominal pain, constipation, and diarrhea, and injection site reactions (with sc administration).

For the most frequently reported treatment emergent adverse events (TEAEs) ( $\geq 10\%$  of subjects), the highest incidence of first occurrence was observed within Cycles 1 and 2, after which time the frequencies decreased over subsequent treatment cycles. Within the cycle, the hematological events tended to occur across the first 3 to 4 weeks of the cycle, whereas the events associated with the administration of azacitidine tended to occur in the first week. These findings suggested a lack of cumulative toxicity and that adverse events (AEs) of azacitidine attenuate over time.

In general, no clinically relevant differences were seen when the safety data were analyzed for age, gender, or MDS subtypes. The most common adverse reactions can be managed through delays or dose decrease of azacitidine and/or supportive measures.

*Adult population with MDS, chronic myelomonocytic leukemia (CMML) and AML (20% to 30% marrow blasts)*

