survival. Azacitidine was administered at a subcutaneous dose of 75 mg/m^2 daily for 7 days, followed by a rest period of 21 days (28-day treatment cycle) for a median of 9 cycles (range = 1 to 39) and a mean of 10.2 cycles. Within the intent to treat population (ITT), the median age was 69 years (range 38 to 88 years). In the ITT analysis of 358 subjects (179 azacitidine and 179 CCR), azacitidine treatment was associated with a median survival of 24.46 months versus 15.02 months for those receiving CCR treatment, a difference of 9.4 months, with a stratified log-rank p-value of 0.0001. The hazard ratio (HR) for the treatment effect was 0.58 (95% confidence interval [CI]: 0.43, 0.77). The two-year survival rates were 50.8% in subjects receiving azacitidine versus 26.2% in subjects receiving CCR (p < 0.0001) (Fenaux, 2009). In this trial the “HI and better” response using IWG 2006 was 36.4% similar to what has been demonstrated in Sekeres (2014) with an ORR (CR, mCR, PR, HI) of 36% after four cycles of azacitidine monotherapy. Data from the AZA-PH-GL-2003-CL-001 survival study with azacitidine in higher-risk MDS subjects found, from analysis of pretreatment bone marrow methylation density, that the overall survival (OS) benefit observed with azacitidine versus CCR was independent of the methylation status of the 5 genes analyzed (CDKN2B [p15], SOCS1, CDH1 [E-cadherin], TP73, and CTNNA1 [α-catenin]). However, increasing methylation was associated with worse OS. Subjects with lower levels of methylation treated with azacitidine had the best OS, suggesting that they may derive greater benefit from azacitidine.

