3. OBJECTIVES

Primary objectives

- To evaluate the efficacy of subcutaneous azacitidine in combination with durvalumab as compared to subcutaneous azacitidine alone in the defined study population.

Secondary objectives

- To assess the safety and tolerability of subcutaneous azacitidine in combination with durvalumab as compared to subcutaneous azacitidine alone in the defined study population.
- To assess the pharmacokinetics (PK) of durvalumab when given in combination with subcutaneous azacitidine in the defined study population.

CCI

[Redacted content]

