5.1.3. Calculation of Cycles

The start date of each treatment cycle will be calculated based on study drug exposure records for each subject. The start date of the first cycle will be the date when the subject receives any dose of study drug. First dose date of Durvalumab infusion or azacitidine injection in each cycle will be considered as the start of the cycle.

Once the start dates, eg, $S_1, S_2, S_3 \dots$ are calculated, the end date of each cycle is calculated as the day before the start date of the following cycle, ie, $E_i = S_{i+1} - 1$. The last cycle in the treatment

phase is defined as the cycle with the last dose of any study drug. For the last cycle, the end date will be the last dose date plus 28 days or the death date, whichever is earlier.

The cycle number for each date of interest, eg, AE or lab, will be calculated based on the cycle window set by their start and end dates. If a date is on or after S_i and before S_{i+1} , the corresponding cycle number will be i .

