12.1. Adverse Events

All safety analyses will be conducted using the Safety Population. All analyses will be presented by disease cohort and treatment arm within each disease cohort. Adverse events will be coded according to the MedDRA Version 19.0 or higher. The intensity of AEs will be graded according to the Common Terminology Criteria for Adverse Events (CTCAE) Version 4.03 or higher.

If a subject experiences multiple AEs under the same PT (SOC), then the subject will be counted only once for that PT (SOC). If a subject experiences the same AE more than once with a different intensity grade, then the event with the highest grade will be tabulated in “by grade” tables. In addition, AEs with a missing intensity will be presented in the summary table as an intensity category of “Missing” and will not be imputed.

Treatment emergent adverse events (TEAEs) are defined as AEs **occurring** or worsening on or after the date of the first dose of the study treatment (durvalumab or azacitidine) and within 90 days after last dose of durvalumab or 28 days after last dose of azacitidine, **as well as those serious TEAEs made known to the investigator at any time thereafter that are suspected of being related to study treatment**. A treatment-related TEAE is defined as a TEAE where the causal relationship was assessed by the investigator as “Suspected”. If the relationship between a TEAE and a study drug is missing, the TEAE will be considered to be related to the study treatment.

Tables summarizing the incidence of TEAEs by disease cohort and treatment arm will be generated with the following:

- TEAEs;
- TEAEs related to azacitidine, durvalumab and azacitidine and/or durvalumab;
- TEAEs of CTCAE grade 3
- TEAEs of CTCAE grade 4
- TEAEs of CTCAE grade 3 or 4;
- TEAEs related to azacitidine, durvalumab and azacitidine and/or durvalumab with CTCAE grade 3
- TEAEs related to azacitidine, durvalumab and azacitidine and/or durvalumab with CTCAE grade 4
- TEAEs related to azacitidine, durvalumab and azacitidine and/or durvalumab with CTCAE grade 3 or 4;
- TEAEs with CTCAE grade 5;

- TEAEs with CTCAE grade 5 related to azacitidine, durvalumab and azacitidine and/or durvalumab;
- Serious TEAEs;
- Serious TEAEs related to azacitidine, durvalumab and azacitidine and/or durvalumab;
- TEAEs leading to discontinuation of azacitidine, durvalumab and azacitidine and/or durvalumab;
- TEAEs leading to dose reduction of azacitidine;

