- TEAEs leading to dose interruption of azacitidine, durvalumab and azacitidine and/or durvalumab;
- TEAEs leading to infusion interruption of durvalumab.

As well as

- TEAEs by cycle of onset;
- Serious TEAEs by cycle of onset;
- TEAEs related to azacitidine, durvalumab and azacitidine and/or durvalumab, by cycle of onset;
- TEAEs of CTCAE grade 3 by cycle of onset
- TEAEs of CTCAE grade 4 by cycle of onset;
- TEAEs of CTCAE grade 3 or 4 by cycle of onset;
- TEAEs by maximum CTCAE grade;
- TEAEs related to azacitidine, durvalumab and azacitidine and/or durvalumab, by maximum CTCAE grade;
- Common ($\geq 10\%$) TEAEs;
- Common ($\geq 10\%$) TEAEs related to azacitidine, durvalumab and azacitidine and/or durvalumab;
- By age category: <65 , $65-74$, ≥ 75
- By gender

Unless otherwise stated, TEAEs will be presented by MedDRA SOC and PT. To facilitate clinical study report writing the following tables will be produced

- TEAEs by PTs
- TEAEs by SOCs
- TEAEs related to azacitidine, durvalumab and azacitidine and/or durvalumab by PTs
- TEAEs related to azacitidine, durvalumab and azacitidine and/or durvalumab by SOCs
- TEAEs of CTCAE Grade 3 or 4 by PTs, by Grade (3 and 4 separately) and combined (3 or 4 combined)

- TEAEs of CTCAE Grade 3 or 4 by SOCs, by Grade (3 and 4 separately) and combined (3 or 4 combined)
- TEAEs related to azacitidine, durvalumab and azacitidine and/or durvalumab of CTCAE Grade 3 or 4 by PTs, by Grade (3 and 4 separately) and combined (3 or 4 combined)
- TEAEs related to azacitidine, durvalumab and azacitidine and/or durvalumab of CTCAE Grade 3 or 4 by SOCs, by Grade (3 and 4 separately) and combined (3 or 4 combined)

All deaths, on treatment deaths, off treatment deaths and causes of death will be summarized. On treatment deaths are defined as deaths occurring within 90 days after the last dose of durvalumab or 28 days after last dose of azacitidine. Off treatment death are defined as deaths occurring after that period. These summaries will be based on the death eCRF page.

Individual subject listing of AEs will be presented. In addition, the following tabulated lists will be provided:

- Listing of SAE;
- Listing of TEAEs leading to permanent withdrawal of any study drug
- Listing of all TEAEs with outcome of death
- Listing of all subjects who died

Adverse events of special interests (AESI)

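### Safety counting windows differ by arm (90 days after durvalumab, 28 after azacitidine), and no cumulative TEAE or on-treatment-death table on a common window is planned

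*SAP*

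**What the plan says.** SAP 12.1 counts an adverse event as treatment-emergent from the first dose until "within 90 days after last dose of durvalumab or 28 days after last dose of azacitidine". It adds related serious events with no time limit: "as well as those serious TEAEs made known to the investigator at any time thereafter that are suspected of being related to study treatment". Deaths are split by the same limits: "On treatment deaths are defined as deaths occurring within 90 days after the last dose of durvalumab or 28 days after last dose of azacitidine"; later deaths are off treatment. All these tables are by cohort and arm. Arm B receives azacitidine only, so the 90-day limit can apply only in Arm A.

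SAP section 3 makes the between-arm comparison a secondary objective: "To assess the safety and tolerability of subcutaneous azacitidine in combination with durvalumab as compared to subcutaneous azacitidine alone".

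Protocol 10.1 sets matching drug-specific periods for recording adverse events, extended to the Treatment Discontinuation Visit if that is later.

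SAP 12.1 lists cumulative tables (overall, Grade 3/4, Grade 5, serious and others), tables by cycle of onset, and separate summaries of adverse events of special interest (AESIs) with rates per 100 person-years. None of the cumulative TEAE tables, and no on-treatment death table, uses one post-treatment window for both arms.

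SAP 12.1 joins the two limits with *or* and does not say which governs. SAP 8.1 and 9.1 use the later date for exposure and concomitant medication. The later date is assumed here.

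**The concern.** A crude percentage of subjects with an event depends on how long each subject is counted. If one arm is counted for longer after treatment stops, its percentage rises even when the true risk is the same. Here the arm counted for longer is the experimental one, so the tables would tend to show more TEAEs and more on-treatment deaths with the combination for a reason unrelated to toxicity. Nothing in the tables shows this; a reader would have to work it out from listings and exposure summaries. At stake is how the safety comparison is read, not the primary efficacy result.

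**Working it through.** The plan states no figure on this point, so there is none to reproduce. The check has two parts: the length of the gap, which is arithmetic, and its effect, which is an illustration.

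**Length of the gap.** Durvalumab is given on Day 1 of each 28-day cycle (Protocol 7.2.1.2) and azacitidine on Days 1 to 7 (Protocol Table 3). Counting from Day 1 of the last durvalumab cycle:

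- Durvalumab limit: 1 + 90 = Day 91.
- Azacitidine limit after k further azacitidine-only cycles: 7 + 28 + 28k = Day 35 + 28k.
- Gap = max(0, 56 − 28k): 56 days if both stop in the same cycle, 28 after one more cycle, 0 from two more.
- If durvalumab is the last drug given (Protocol 3.2.2 allows either drug alone), the gap against 28 days after the last dose of any drug is up to 91 − 29 = 62 days.

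**Hand calculation for deaths.** Assume the same constant death hazard in both arms, h = ln 2 / median OS, with 30.4375 days per month. The azacitidine medians are 10.4 months for AML (Protocol 1.3.3) and 24.46 months for MDS (Protocol 1.3.2). With cycle 6 as the last cycle for both drugs, the window ends 140 + 90 = 230 days after the first dose in Arm A and 140 + 34 = 174 days in Arm B. P = 1 − exp(−h × days):

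| Cohort | Arm B | Arm A | Difference |
|---|---|---|---|
| AML | 31.7% | 39.6% | +7.9 points |
| MDS | 15.0% | 19.3% | +4.3 points |

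Moving the last cycle from 3 to 12 changes the difference from +9.5 to +5.5 points (AML) and from +4.7 to +3.7 (MDS).

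**Simulation with staggered stopping.** One million subjects per case; exponential death as above; exponential stopping for other reasons with an assumed median of 4, 6 or 9 months; both drugs stopping in the same cycle. The 15-month enrolment gives a uniform cut-off of 6–21 months at the primary analysis and 12–27 months at the later one. On-treatment deaths, Arm B / Arm A, %:

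| Cohort, cut-off | 4 months | 6 months | 9 months |
|---|---|---|---|
| AML, 6–21 | 28.9 / 36.2 | 34.8 / 40.8 | 40.2 / 44.9 |
| AML, 12–27 | 30.4 / 38.3 | 37.8 / 44.5 | 45.1 / 50.5 |
| MDS, 6–21 | 14.1 / 18.0 | 17.5 / 20.7 | 20.7 / 23.2 |
| MDS, 12–27 | 15.1 / 19.4 | 19.6 / 23.3 | 24.2 / 27.3 |

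From unrounded results the excess is 4.7–7.9 points in AML (× 55 = 2.6–4.3 deaths) and 2.5–4.2 points in MDS (× 36 = 0.9–1.5 deaths).

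**Sensitivity of the death figures.**

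- MDS with median treatment of 9 cycles, as in the earlier trial in Protocol 1.3.2: 9 × 28 / 30.4375 = 8.28 months. This implies a non-death stopping median of 12.5 months (1/8.28 − 1/24.46 = 1/12.5). Results are 23.0 / 25.0% and 27.8 / 30.3%, an excess of 2.0–2.5 points.
- If 20% of Arm A continue azacitidine alone for two or more cycles, the excess scales by 0.8: 3.8–6.3 points (AML), 2.0–3.4 (MDS, 4–9 month cases).
- Protocol 1.3.3 also gives 24.5 months for AML with 20% to 30% blasts. That is close to the MDS hazard, so the AML excess would be about 2.5–4.2 points (× 55 = 1.4–2.3 deaths).

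**TEAEs.** First-event rates are assumed; timing matters. Protocol 1.3.1 reports that "the highest incidence of first occurrence was observed within Cycles 1 and 2", which favours the front-loaded rows. AML, 6–21 months, Arm B / Arm A, %:

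| Monthly rate | 4 months | 6 months | 9 months |
|---|---|---|---|
| 0.5 for 56 days, then 0.05 | 59.3 / 63.4 | 61.4 / 64.4 | 63.1 / 65.3 |
| 1.0 for 56 days, then 0.1 | 81.4 / 85.0 | 83.0 / 85.5 | 84.2 / 86.0 |
| Flat 0.10 | 31.7 / 38.7 | 36.3 / 41.8 | 40.3 / 44.4 |
| Flat 2.0 (near-universal) | 95.1 / 96.7 | 95.6 / 96.7 | 96.0 / 96.7 |

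Pooling both cut-offs, and including the 9-cycle case for MDS, the excess is 1.8–4.3 points (AML) and 1.5–4.8 (MDS) when front-loaded, 4.1–7.3 and 3.9–8.7 at flat 0.10, and 0.6–1.8 for near-universal events.

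**With a common window.** Counting both arms to 28 days after the last dose of any study drug ends both at Day 35 when the drugs stop together, and the excess under equal hazards is 0 (cycle 6: AML 31.7% in both arms, MDS 15.0% in both).

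**The case against.** The strongest reply is that the plan already contains most of what a careful reader needs.

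- **All deaths by arm (SAP 12.1) and overall survival (SAP 10.2)** are cumulative and use one rule in both arms. This stands: only the on/off-treatment label is affected, and no death is gained or lost.
- **The windows follow the protocol's drug-specific recording periods**, and 90 days suits late immune-mediated events. This stands as a reason to keep the 90-day tables. It does not make them comparable between arms.
- **SAP 8.1 shows the unequal exposure window openly by arm, and AESIs get person-year rates.** If that exposure is the denominator, those rates would be fair under a constant hazard, and AESIs include myelosuppression, infections, bleeding, cardiac and gastrointestinal events. This is real but partial: SAP 12.1 does not define the person-time, and overall, serious and Grade 5 TEAEs get no such rate.
- **By-cycle tables.** In SAP 5.1.3 the cycle number "will be calculated based on the cycle window set by their start and end dates", and "For the last cycle, the end date will be the last dose date plus 28 days or the death date, whichever is earlier". On the natural reading these tables stop 28 days after the last dose of any drug in both arms. They cover all, serious, related and Grade 3/4 TEAEs, but are not cumulative, and the general ones omit Grade 5. On that reading Arm A events on days 29 to 90 belong to no cycle, so the by-cycle and overall tables will not reconcile. Another sentence there can be read as putting later events in the last cycle; the tables would then carry the unequal window too.
- **Related serious events** count without limit in both arms, which narrows the gap for that table.
- **The AML survival input is the shorter of two the protocol reports.** Fair; the alternative roughly halves the AML figure.

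**Conclusion.** The concern holds. The windows differ by arm, the tables compare arms, and no cumulative TEAE or on-treatment-death table uses a common post-treatment window. The 56-day gap when both drugs stop together is exact, reading the limits as the later of the two dates. The percentage-point figures are illustrations: they assume equal constant death hazards, assumed stopping times and event rates, and both drugs stopping in the same cycle. Within those limits the effect is a few percentage points, larger for AML deaths and small for near-universal events. Safety is descriptive (SAP 12) and no decision rule rests on these tables, so this is an inexpensive improvement that should be made, not an error that changes the primary result.

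**What to change.** In SAP 12.1:

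1. Keep the 90-day tables as the durvalumab safety profile.
2. Add cumulative by-arm tables of overall, Grade 3/4, Grade 5 and serious TEAEs with onset up to 28 days after the last dose of any study drug, with the same rule in both arms.
3. Add deaths within 28 days and within 90 days of the last dose of any study drug in both arms, using death dates from survival follow-up (Protocol 3.2.3.2).
4. Footnote the window applied in each arm, including that the later limit governs if that is the intention.

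A common 90-day TEAE table is not feasible, because Arm B events are generally recorded only to day 28 (Protocol 10.1). The cost is SAP wording, footnotes and a few tables from data already collected. The drawback is that late immune-mediated events appear only in the 90-day tables, which is why those should stay.

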12.2. Clinical Laboratory Evaluations

Descriptive statistics of observed and change from baseline values will be presented.

Clinical laboratory values will be graded according to CTCAE Version 4.03 or higher for applicable tests. Baseline grade and worst grade during treatment for selected laboratory results will be summarized. Shifts from baseline to the worst grade observed during the treatment for selected laboratory results will also be provided.

Clinically significant hematologic and nonhematologic laboratory abnormalities that meet Grade 3 or Grade 4 criteria according to CTCAE Version 4.03 will be listed and summarized. Listings of clinical laboratory data from central laboratory with abnormal flags will be provided by subjects and tests.

Listings of clinical laboratory data from central laboratory with abnormal flags will be provided by subjects and tests. Listings will also be provided for the local laboratory data.

CCI

12.4. Vital Sign Measurements

For vital signs with shifts from baseline to worst during treatment (below, within, and above the normal ranges) will be displayed in cross-tabulations. Summary statistics (N, Mean, STD, median, Q1, Q3 Min, and Max) of observed and change from baseline values will be presented.

Normal ranges are defined as follows:

- Systolic blood pressure (SBP) → Normal (100 – 140 mm Hg, inclusive)
- Diastolic blood pressure (DBP) → Normal (60 – 90 mm Hg, inclusive)
- Body temperature → Normal (35 – 38°C, inclusive)
- Pulse → Normal (60 – 100 bpm, inclusive)
- Respiration → Normal (12 – 20 BPM, inclusive).

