### **6.6.3. Physical Examination, Vital Signs and Weight**

The following routine assessments are to be performed as specified below. Significant findings must be included on the appropriate eCRF and in the subject's source documents:

- Pulse
- Blood pressure (systolic and diastolic)
- Physical examination
- Body temperature
- Respiratory rate
- Body weight

The above assessments are to be performed during screening, on Day 1 of each cycle before administering the study IP, at the Treatment Discontinuation Visit, and at the 28day/90-day Safety Follow-Up Visits, as applicable. At every visit during treatment phase (Days 8, 15 and 22 for Cycles 1 and 2 and Days 1 and 15 for Cycle 3 onwards), vital signs that include blood pressure, pulse, body temperature and respiratory rate will be assessed.

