### 7.2.1.3. Monitoring of Durvalumab Dose Administration

Subjects will be monitored during and after infusion of durvalumab. Vital signs will be measured within 30 minutes prior to durvalumab administration, every 15 minutes ( $\pm$  5 minutes) during durvalumab administration, at the end of the durvalumab infusion ( $\pm$  5 minutes), and at 30 minutes ( $\pm$  5 minutes) and 60 minutes ( $\pm$  5 minutes) postinfusion of durvalumab, followed by a 2-hour ( $\pm$  15 minutes) period of observation.

In the event of a  $\leq$  Grade 2 infusion-related reaction, the infusion rate of durvalumab may be decreased by 50% or interrupted until resolution of the event (up to 4 hours) and re-initiated at 50% of the initial rate until completion of the infusion. For subjects with a  $\leq$  Grade 2 infusion-related reaction, subsequent infusions may be administered at 50% of the initial rate.

Acetaminophen and/or an antihistamine (eg, diphenhydramine) or equivalent medications per institutional standard may be administered at the discretion of the Investigator. If the infusion-related reaction is  $\geq$  Grade 3 in severity, IP will be discontinued.

As with any antibody, allergic reactions to dose administration are possible. Appropriate drugs and medical equipment to treat acute anaphylactic reactions must be immediately available, and study personnel must be trained to recognize and treat anaphylaxis. The study site must have immediate access to emergency resuscitation teams and equipment in addition to the ability to admit subjects to an intensive care unit if necessary.

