4. INVESTIGATIONAL PLAN

4.1. Overall Study Design and Plan

This is a Phase 2, multicenter, randomized, parallel-group, open-label study evaluating the efficacy and safety of subcutaneous azacitidine either alone or in combination with durvalumab in two separate cohorts. Cohort 1 comprises subjects with previously untreated myelodysplastic syndrome (MDS) Revised International Prognostic Scoring System (IPSS-R) intermediate risk (in combination with more than 10% bone marrow (BM) blasts or poor or very poor IPSS-R cytogenetic risk), or IPSS-R high or IPSS-R very high risk, who are not eligible for HSCT. Cohort 2 comprises subjects with previously untreated acute myeloid leukemia (AML) (de novo AML with $\geq 20\%$ blasts) or secondary AML, as per WHO classification, who are elderly (≥ 65 years) and not eligible for HSCT, with intermediate or poor cytogenetic risk.

Subjects will be randomized (1:1 ratio) to receive one of the two treatment arms:

- Arm A (subcutaneous azacitidine plus durvalumab)
- Arm B (subcutaneous azacitidine alone)

[figure not shown]
The randomization process will aim to balance prognostic factors between study arms. For both cohorts (MDS and AML), subjects will be randomized and stratified according to their cytogenetic risk:

- Intermediate versus poor for AML ([Appendix 17.5](#)),
- Very good, good and intermediate versus poor and very poor for MDS ([Appendix 17.4](#)).

The randomized study will be conducted in 2 stages, with an interim analysis for futility purpose for each of the 2 disease cohorts determining whether that cohort proceeds to Stage 2. The interim analysis will be conducted in the MDS cohort when the first 30 subjects have completed 6 cycles of treatment unless they have established an earlier response (CR, mCR, PR or HI) or discontinued due to death or disease progression while the interim analysis in the AML cohort will be conducted when the first 50 subjects have completed 6 cycles of treatment unless they have established an earlier response (CR or CRi) or discontinued due to death or disease progression. Subjects assigned to Arm A, who received less than 3 cycles of durvalumab and continued under azacitidine monotherapy are to be excluded from the interim analysis.

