12. SAFETY ANALYSIS

This section defines the safety parameters for the study. All summaries of safety data will be conducted using the Safety Population. Descriptive statistics will be provided by disease cohort and treatment arm.

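### SAP 12.4 does not say which readings feed the worst-on-treatment vital-sign table, and only Arm A has serial infusion readings, so reading count alone could raise Arm A's out-of-range counts

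*SAP*

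**What the plan says.** SAP 12.4 plans a shift table for blood pressure, temperature, pulse and respiration against fixed normal ranges: "For vital signs with shifts from baseline to worst during treatment (below, within, and above the normal ranges) will be displayed in cross-tabulations". Section 12 applies this to the Safety Population and adds: "Descriptive statistics will be provided by disease cohort and treatment arm". Section 12.4 does not limit the table to scheduled visits, mention infusion monitoring, or define the on-treatment window for vital signs. Protocol 9.7, which plans a normal/abnormal table before and after the start of treatment, has no such limit either.

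Protocol 6.6.3 gives both arms the same routine schedule: "on Day 1 of each cycle before administering the study IP", and at the other treatment visits ("Days 8, 15 and 22 for Cycles 1 and 2 and Days 1 and 15 for Cycle 3 onwards"), where "vital signs that include blood pressure, pulse, body temperature and respiratory rate will be assessed".

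Protocol 7.2.1.3 adds monitoring that applies only to durvalumab recipients: "Vital signs will be measured within 30 minutes prior to durvalumab administration, every 15 minutes" during the infusion, then at its end and 30 and 60 minutes afterwards. The Table of Events footnotes repeat this for Day 1 of every cycle.

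The comparison serves a stated secondary objective in SAP 3: "To assess the safety and tolerability of subcutaneous azacitidine in combination with durvalumab as compared to subcutaneous azacitidine alone".

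**The concern.** A worst value is an extreme, and an extreme over more readings is at least as extreme as one over fewer. If a programmer applies SAP 12.4 literally to a dataset that holds the infusion readings, each Arm A subject has over three times as many chances to cross a limit as each Arm B subject. The table would then mix measurement frequency with any real drug effect, and an excess in Arm A could be taken for poorer tolerability. At stake is the reading of one comparative safety table. The primary analysis is not affected.

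**Working it through.** The plan states no figure on this point, so there is none to reproduce.

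**Counting scheduled readings over six cycles** (the recommended minimum)

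- Routine, both arms (Protocol 6.6.3): Cycles 1–2 have Days 1, 8, 15 and 22, so 2 × 4 = 8. Cycles 3–6 have Days 1 and 15, so 4 × 2 = 8. Total 16.
- Infusion, Arm A only (Protocol 7.2.1.2 and 7.2.1.3, infusion of about one hour): 1 before, 3 during (15, 30 and 45 minutes), 1 at the end, 2 afterwards. That is 7 per infusion, 6 of them beyond the pre-dose reading.
- Arm A total: 16 + 6 × 6 = 52 if the pre-infusion reading also serves as the routine Day 1 reading (52/16 = 3.25 times Arm B). If the two are taken separately, 16 + 6 × 7 = 58 (3.6 times).

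Under SAP 5.3.4 the Cycle 1 pre-dose reading will usually be the baseline. Leaving it out gives 51 v 15 and does not change the argument.

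**Upper extreme: independent readings, same distribution in both arms**

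P(at least one out of range) = 1 − (1 − p)^n, where p is the chance that a single reading is out of range. The documents do not give p; it is assumed.

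- p = 2%: Arm B 1 − 0.98^16 = 27.6%; Arm A 1 − 0.98^52 = 65.0%.
- p = 5%: Arm B 1 − 0.95^16 = 56.0%; Arm A 1 − 0.95^52 = 93.1%.

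**Correlated readings**

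Readings minutes apart in one person are not independent. I simulated a normal variable with total variance 1, split into subject, day and single-reading parts. Each arm had the same 16 routine days, Arm A had 6 extra readings on each of six Day 1s, there was no drug effect, and one one-sided limit was set to give p. The variance shares are assumptions.

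| Subject / day / reading share | p | Arm B | Arm A | Excess (points) |
|---|---|---|---|---|
| 0.70 / 0.20 / 0.10 | 2% | 11.1% | 15.2% | 4.1 |
| 0.70 / 0.20 / 0.10 | 5% | 22.2% | 28.5% | 6.3 |
| 0.50 / 0.30 / 0.20 | 2% | 15.9% | 24.3% | 8.4 |
| 0.50 / 0.30 / 0.20 | 5% | 30.9% | 42.5% | 11.6 |
| 0.35 / 0.30 / 0.35 | 2% | 19.2% | 33.0% | 13.7 |
| 0.35 / 0.30 / 0.35 | 5% | 37.5% | 55.2% | 17.7 |

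The spurious excess therefore runs from about 4 to 18 points. It grows with the single-reading share: at 0.40 (0.30 / 0.30 / 0.40) and p = 5% it is just under 20. It vanishes when that share is zero, that is, when all readings on one day are identical.

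**After restriction to common visits**

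The count is 16 v 16, and the excess due to reading count is zero for equal time on treatment. Equal time is not assured. SAP 8.1 counts exposure to 28 days after the last azacitidine dose in Arm B, but in Arm A to the later of that date and 90 days after the last durvalumab dose. Used as the vital-sign window, that would let a 90-day follow-up reading into Arm A only.

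**The case against.** The strongest reply is that the premise is not in the documents. Nothing says that each infusion reading is entered in the eCRF or reaches the analysis data. Protocol 6.6.3 requires only significant findings on the eCRF. In the Table of Events the vital-signs row follows the visits, and infusion monitoring appears only in a footnote on drug administration. The SAP also leaves some detail to table shells and a derived dataset specification, where time points might be chosen. This stands, and it makes the point conditional. It does not remove it: the infusion readings are protocol-specified vital signs, and SAP 12.4 does not exclude them. If only significant findings are recorded, Arm A still has more occasions to produce one.

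Three stronger inferences are tempting, and the documents support none of them.

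- A reader might infer that the table is certain to be biased, or that any Arm A excess is pure chance. Neither follows, because data capture is unstated and a real infusion effect could contribute to an excess.
- A reader might take 93% v 56% as the expected size. It requires independence between readings 15 minutes apart, which is implausible.
- A reader might infer that the plan cannot detect a durvalumab infusion effect at all. That holds only within this one table. SAP 12.1 summarises infusion-related, hypersensitivity and anaphylactic reactions as AESIs, and events leading to infusion interruption. SAP 8.7 summarises infusion interruptions.

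The argument also does not extend to the observed-value and change-from-baseline statistics in SAP 12.4. A mean does not drift outwards with the number of readings as an extreme does.

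**Conclusion.** The point holds in conditional form and is minor. The unequal schedule and the absence of an eligibility rule in SAP 12.4 are in the documents. If the infusion readings are in the dataset, the bias runs towards more out-of-range subjects in Arm A. Its size cannot be taken from the documents. The range of about 4 to 18 percentage points rests on six cycles of treatment, p of 2% to 5%, and the assumed variance shares. Arm A subjects who stop durvalumab and continue azacitidine have fewer extra readings, which reduces the excess. The table carries no test and no decision rule, so only its interpretation is affected.

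**What to change.** In SAP 12.4:

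1. Build the between-arm baseline-to-worst shift table only from routine visits scheduled in both arms: pre-dose Day 1, Days 8, 15 and 22 of Cycles 1–2, and Day 15 of later cycles where scheduled.
2. Define the on-treatment window for this table in the same way for both arms, so that the 90-day and 28-day follow-up periods do not make it unequal.
3. Show Arm A's infusion and post-infusion readings in a separate Arm A table.
4. Reconcile the schedule from Cycle 7 on: the Table of Events lists vital signs on Day 1 only, whereas Protocol 6.6.3 has Days 1 and 15 from Cycle 3 onwards. This affects both arms alike, but the filter needs one answer.

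The cost is a few lines of SAP text, a time-point filter and one extra table. No data are lost. If the infusion readings were never captured, the filter in item 1 does no harm.
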